HALT-C Ancillary Study PROPOSAL

Part I

Proposal Name: Validation of Cirrhosis Risk Score in Patients with Chronic Hepatitis C

Proposal PI: [name], Celera

HALT-C PI: [name]

Funding Agency and Review Body (e.g., NIDDK; my university/GAC): Celera Diagnostics

I agree to follow HALT-C Policies and Procedures when conducting this study. I acknowledge that the data obtained from this study will belong to the NIH and will be placed in the HALT-C database for use by other investigators. I understand that I cannot begin experiments using HALT-C specimens/data until I receive approval from the HALT-C Steering Committee and funding from the Scientific Review Body for my proposal. I also understand that the data analysis for this proposal will be performed by NERI (unless otherwise approved by the HALT-C study) and that protocols approved by the HALT-C Steering Committee will be placed on the HALT-C Restricted Website.

_____ Proposal Principal Investigator	_____ Date
_____ HALT-C Principal Investigator Date	_____ Date

Protocol Part II (4 page limit, single space)

1. Aims/hypotheses

Hypothesis

- Genetic factors play a role in fibrosis progression and adverse clinical outcomes (hepatic decompensation and hepatocellular carcinoma [HCC]) in patients with hepatitis C

Primary aims

- To validate the Caucasian cirrhosis risk score (CRS) in predicting the risk of cirrhosis in HALT-C non-Hispanic Caucasian patients and to evaluate the accuracy of the Caucasian CRS in predicting the risk of progression from advanced fibrosis to cirrhosis and the risk of development of cirrhosis complications.
- To evaluate the Caucasian CRS in predicting the risk of cirrhosis and cirrhosis complications in HALT-C African American patients.

Secondary aims

- To validate the African American CRS (when available) in HALT-C African American patients.
- To evaluate the combined utility of CRS and non-invasive indices of hepatic fibrosis such as AST-platelet ratio index (APRI) and the HALT-C cirrhosis prediction index.

2. Background/rationale

- The fibrosis progression rate is highly variable among patients with chronic hepatitis C. Overall it is estimated that only about 20% of patients with chronic hepatitis C will progress to cirrhosis after 20 years of infection¹. Previously identified clinical risk factors for fibrosis progression include male gender, excessive alcohol use, older age at the time of infection and the presence of steatosis on liver biopsy². However, many patients with these characteristics have mild disease and some patients without these factors have cirrhosis³.
- Besides clinical factors, recent studies suggested that host genetic factors, such as single nucleotide polymorphisms (SNPs) could play an important role in determining the risk for fibrosis progression^{4,5}.
- In the past 5 years, Celera Diagnostics has worked with 5 major academic centers in the US and enrolled 1,468 patients (984 Caucasians, 293 African Americans and 191 other races) with chronic hepatitis C (CHC). From a functional genomic scan of 25,000 SNPs, 361 SNPs were selected for the signature building based on their significant association with fibrosis risk in two large cohorts⁵. Using a 'machine learning' approach, a signature consisting of 7 markers most predictive of cirrhosis risk in Caucasian patients was developed, and Cirrhosis-Risk-Score (CRS) was calculated to determine the risk for each patient.
- The area-under-the-ROC-curves (AUROC) of the CRS in Caucasian patients was 0.75 in the Training cohort. In the Validation cohort, AUROC was only 0.53 for clinical risk factors, increased to 0.73 for CRS, and to 0.76 when CRS was combined with clinical risk factors. A CRS low-cutoff of <0.50 to identify low-risk patients would misclassify only 10.3% of high-risk patients, while a high-cutoff of >0.73 to identify high-risk patients would misclassify 22.3% of low-risk patients (Table 1).

Table 1: Predictive Values of CRS

5A. Training Cohort

CRS	All Patients	Low-Risk (Stage 0) (N=157)	High-Risk (Stage 3-4) (N=263)	NPV	PPV	Sensitivity	Specificity	Misclassifying Rate ^a
< 0.10	4 (1.0%)	4	0	100.0%		100.0%	2.5%	0.0%
< 0.20	18 (4.3%)	16	2	88.9%		99.2%	10.2%	0.8%
< 0.30	30 (7.1%)	27	3	90.0%		98.9%	17.2%	1.1%
< 0.40	55 (13.1%)	46	9	83.6%		96.6%	29.3%	3.4%
< 0.50 ^b	98 (23.3%)	71	27	72.4%		89.7%	45.2%	10.3%
> 0.70 ^b	194 (46.2%)	35	158		81.4%	60.1%	77.7%	22.3%
> 0.75	155 (36.9%)	28	127		81.9%	48.3%	82.2%	17.8%
> 0.80	67 (16.0%)	11	56		83.6%	21.3%	93.0%	7.0%
> 0.85	55 (13.1%)	9	46		83.6%	17.5%	94.3%	5.7%
> 0.90	10 (2.4%)	0	10		100.0%	3.8%	100.0%	0.0%

5B. Validation Cohort

CRS	All Patients	Low-Risk (Stage 0) (N=14)	High-Risk (Stage 3-4) (N=140)	NPV	PPV	Sensitivity	Specificity	Misclassifying Rate ^a
< 0.10	1 (0.6%)	1	0	100.0%		100.0%	7.1%	0.0%
< 0.20	5 (3.2%)	3	2	60.0%		98.6%	21.4%	1.4%
< 0.30	14 (9.1%)	6	8	42.9%		94.3%	42.9%	5.7%
< 0.40	16 (10.4%)	6	10	37.5%		92.9%	42.9%	7.1%
< 0.50 ^b	23 (14.9%)	6	17	26.1%		87.9%	42.9%	12.1%
> 0.70 ^b	78 (50.6%)	3	75		96.2%	53.6%	78.6%	21.4%
> 0.75	57 (37.0%)	3	54		94.7%	38.6%	78.6%	21.4%
> 0.80	31 (20.1%)	1	30		96.8%	21.4%	92.9%	7.1%
> 0.85	26 (16.9%)	1	25		96.2%	17.9%	92.9%	7.1%
> 0.90	4 (2.6%)	0	4		100.0%	2.9%	100.0%	0.0%

a. The low cutoff was chosen to minimize misclassification of patients at high risk of cirrhosis as being low risk

- b. Using 0.50 and 0.70, 30.5% and 34.5% patients were not classifiable in Training and Validation cohort, respectively.
- Indices derived from routinely available laboratory results have been reported to correlate with advanced fibrosis or cirrhosis on biopsies. These indices include APRI (derived from AST and platelet)⁶ and the HALT-C cirrhosis prediction index (derived from platelet, AST/ALT ratio and INR)⁷.
 - The CRS was developed with the aim to predict the risk of cirrhosis. To date, studies performed by Celera had been cross-sectional studies showing that the CRS correlated with histological cirrhosis with an AUROC of 0.73-0.75. To validate that the CRS can predict the risk of cirrhosis, Celera has embarked on a study involving multiple liver centers to recruit patients who had baseline liver biopsies at early disease stages (F0-F1) and who have undergone serial liver biopsies.
 - The CRS did not use complications of cirrhosis (eg. hepatic decompensation and HCC) as endpoints for the study. It will be interesting to determine if the genes that predict cirrhosis also predict progression to cirrhosis complications.

3. Relations to aims of HALT-C study

The main aim of the HALT-C study is to determine if maintenance interferon therapy can delay disease progression in patients with hepatitis C and advanced fibrosis/cirrhosis, who failed to achieve sustained virologic response to antiviral therapy. Several ancillary studies were designed to examine noninvasive assessment of liver fibrosis, risk factors for cirrhosis as well as progression to decompensated cirrhosis and HCC. This proposal will complement those ancillary studies and will determine if the majority of the HALT-C patients will be predicted to develop cirrhosis based on genetic factors. The application of the Celera CRS to the subset of patients who progressed from bridging cirrhosis at entry to cirrhosis during the course of the HALT-C study will be of particular interest. The Celera CRS was built on data from Caucasian patients, the large number of African Americans with cirrhosis/advanced fibrosis in the HALT-C study provides an opportunity to evaluate the Caucasian CRS for African Americans with hepatitis C.

This proposal will also explore the utility of the Caucasian CRS in predicting decompensated cirrhosis and HCC. Additional discovery work including identification of other genes and formulation of new risk scores may be necessary for the prediction of decompensated cirrhosis and HCC. These new scores will need to be validated in external cohorts.

The current proposal will include exploration of the utility of the Caucasian CRS in predicting decompensated cirrhosis and HCC. A separate proposal will be developed in parallel to conduct additional discovery work to develop risk scores for predicting decompensated cirrhosis and HCC among patients with chronic hepatitis C. It is anticipated that the second proposal will entail more resources and a much longer period of time to complete, including possibly expanding PBMCs from patients who do not have adequate DNA in our repository. The goal is to be ready to launch the second proposal when work related to the first proposal is completed, assuming that the results of the first proposal are positive or encouraging.

4. Study design, experimental groups

Patients

- Non-Hispanic Caucasian and African American patients who participated in the HALT-C Study and who consented to genetic studies, patients of other racial/ethnic groups will not be included as their numbers are too small to generate meaningful data
- This study will include all patients who participated in the randomized phase of HALT-C as well as patients who were responders in the lead-in phase, and will include patients with bridging fibrosis as well as those with cirrhosis

Study design

- 250 ng genomic DNA from each eligible patient will be sent to Celera for genotyping

5. Methods, data usage

Required clinical data from HALT-C DCC

- A defined data set on patients who meet eligibility criteria listed in section 4 and in whom DNA samples are available will be created by NERI and sent to Celera for analysis. The dataset will include:
 - (a) Demographics, duration of HCV infection, alcohol and smoking history, BMI, HCV genotype
 - (b) Baseline information: histology (inflammation, fibrosis and steatosis score, length of biopsy and fragmentation), baseline labs (CBC, liver panel, INR, HCV RNA), baseline ultrasound finding (spleen size), (W24 or R00) EGD findings (presence or absence of varices/portal gastropathy)
 - (c) M24 labs (CBC, liver panel, INR), ultrasound finding (spleen size) and histology (inflammation, fibrosis and steatosis score, length of biopsy and fragmentation)
 - (d) M48 labs (CBC, liver panel, INR), ultrasound finding (spleen size), histology (inflammation, fibrosis and steatosis score, length of biopsy and fragmentation) and EGD findings (presence or absence of varices/portal gastropathy)
 - (e) Occurrence of clinical outcomes
- DNA samples and dataset will be de-identified and coded using subject number only.

Genotyping

- CRS Multiplex Research Prototype: A single tube multiplex PCR-Oligonucleotide Ligation research assay (PCR-OLA) was established to genotype all 7 SNPs in CRS signature plus gender. Each of the eight distinct amplicons is genotyped by an OLA which involves the joining of an Allele-Specific Oligonucleotide containing a complementary sequence tag for a specific oligonucleotide-conjugated Luminex® bead with a Ligation-Specific Oligonucleotide containing a 3' biotin. The ligation products are then hybridized to derivatized Luminex® beads, labeled by the reporter molecule Streptavidin-Phycoerythrin, and analyzed on a Luminex® 100™ system. Genotypes are determined automatically by generic research software that compares the ratio of fluorescent signals between the two alleles.
- Allele Specific PCR: If additional SNPs needed to be genotyped, allele specific PCR will be used. For each SNP, two amplification reactions will be performed, one for each allele. Each PCR reaction contains one of the two allele-specific primers and a common reverse primer. All reactions will be amplified on Applied Biosystems PRISM 7900HT Sequence Detection instrument. For individual DNA, the genotypes will be automatically called by a custom-designed algorithm.

Data analyses

For all the following analyses, CRS value will be calculated using a Naïve Bayes algorithm developed by Celera (see details below). The performance of CRS in HALT-C patients will be evaluated by statistical parameters such as Area under the ROC Curve (AUC), sensitivity, specificity, positive predictive value (PPV), negative predictive value (NPV) etc.

- Stage 1A: Validate the current Caucasian CRS with 7 SNPs plus gender in Caucasian and African American patients from HALT-C trial in predicting
 - Cirrhosis on baseline biopsy
 - Progression to cirrhosis on M24 or M48 biopsy – for those who did not have cirrhosis on baseline biopsy
- Stage 1B: Explore the current Caucasian CRS with 7 SNPs plus gender in Caucasian and African American patients from HALT-C trial in predicting
 - Progression to cirrhosis complications – hepatic decompensation and/or HCC
- Stage 2: Validate the optimized Caucasian CRS (upon availability) in Caucasian and African American patients from HALT-C trial. Celera is performing fine density mapping of CRS signature, in which over 600 SNPs around the original 7 SNPs are being evaluated. These SNPs will be incorporated into the modeling process to obtain a more optimized Caucasian CRS signature. The optimized Caucasian CRS is expected to be available by June 2007.
- Stage 3: Validate the African American CRS (upon availability) in African American patients from HALT-C trial. Currently, Celera has DNA samples from 293 African American (AA) patients enrolled using the same criteria as Caucasian patients. Celera is in the process of identifying SNPs significant in AA population from the genome scan data. Although sample size may be inadequate, Celera will explore the possibility of building the AA CRS signature. The preliminary result is expected to be available in August 2007. If a predictive signature can be identified, its performance will be validated in AA patients from HALT-C trial.
- Stage 4: Evaluate the utility of combining the Celera CRS with age or duration of infection and a cirrhosis index based on laboratory test results at the time of evaluation in predicting cirrhosis.

Naïve Bayes Algorithm (optional)

The value of CRS based on a constellation of 7 SNPs was calculated using a Naïve Bayes formula¹³. Given outcomes $C = \{\text{cirrhosis, no cirrhosis}\}$ and a set of seven predictive SNPs $X = \{X_1, X_2, \dots, X_7\}$, the probability of a patient $S = \{X_1 = x_1, X_2 = x_2, \dots, X_n = x_7\}$ having cirrhosis is computed as follows:

$$\text{CRS} = \frac{0.626 * P(S | \text{cirrhosis})}{0.626 * P(S | \text{cirrhosis}) + 0.374 * P(S | \text{no Cirrhosis})}$$

The conditional probabilities $P(S | \text{cirrhosis})$ and $P(S | \text{no cirrhosis})$, were estimated assuming each SNP was independent of all other SNPs.

The probabilities, $P(X_i = x_i | \text{cirrhosis})$, $P(X_i = x_i | \text{no cirrhosis})$ are the class conditional probabilities for the i th marker X_i with value x_i (each SNP can take the value of '1' or '0' based on the genotypes), given that the patient has cirrhosis or no cirrhosis respectively.

6. Anticipated results

Caucasian patients - We anticipate the vast majority of patients will be predicted to have cirrhosis according to the CRS, and the accuracy will be highest among those with cirrhosis in the baseline biopsy followed by those who progressed from bridging fibrosis on baseline biopsy to cirrhosis on M24 or M48 biopsies or developed clinical outcome by M48, and patients who had bridging fibrosis on baseline biopsy and did not progress to cirrhosis on M24 or M48 biopsies or develop clinical outcome by M48. We anticipate that the current CRS will be more accurate in predicting histological cirrhosis than hepatic decompensation or HCC. The risk score may need to be modified in order to effectively predict cirrhosis complications as well.

Deleted:

African American patients – Due to the genetic variations commonly seen in different races, it is hard to predict the performance of Caucasian CRS in African American patients. The results will be valuable to determine if additional studies are needed to generate a separate signature for African Americans. Data from African American HALT-C patients will also be used to validate the African American CRS when this is available.

Combination of CRS and age (duration of HCV infection) and a cirrhosis index based on laboratory results at the time of evaluation might further improve the accuracy of cirrhosis prediction.

7. Statistical support

Biostatisticians at Celera will perform the analysis, the final results will be verified by statisticians at NERI

8. HALT-C samples to be used in the study (complete Part III: Sample Requirements)

250 ng genomic DNA from each Caucasian and each African American patient in the HALT-C study, who consented to genetic studies and in whom DNA samples are available

9. Financial issues (e.g., cost for data analysis and obtaining samples from Repository)

Celera will cover the costs of identification, retrieval and shipment of samples from the Repository; preparation and transfer of the defined data set, statistical oversight, and coordination of the entire ancillary study.

10. References.

1. Thomas D and Seeff L 2005, Clin Liver Dis 9:383-98
2. Poynard T et al 1997, Lancet 349: 825-832
3. Marcellin P et al 2002, Hepatology 36:S47-56
6. Wai C et al 2003, Hepatology 38: 518-526
7. Lok A et al 2005; Hepatology 42: 282-292

Protocol Part III: Sample Requirements

Visit	Liver # patients, mm*	Blood # patients, ml	Other (describe) # pts, amount
Screen 1			Up to 670 samples of 250 ng genomic DNA from S00 or later visit.
Screen 2			
Baseline			
Lead in			
Week 4			
Week 8			
Week 12			
W16			
Week 20			
Week 24			
Randomized			
Month 9			
Month 12			
Month 15			
Month 18			
Month 21			
Month 24			
Month 27			
Month 30			
Month 33			
Month 36			
Month 39			
Month 42			
Month 45			
Month 48			
Post-treatment

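### The quoted AUROC of 0.73-0.75 is for Stage 3-4 versus Stage 0, so the Stage 1A contrasts within advanced fibrosis can neither confirm nor refute it

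*Protocol*

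**What the plan says.** The first primary aim (protocol section 1) is "To validate the Caucasian cirrhosis risk score (CRS) in predicting the risk of cirrhosis in HALT-C non-Hispanic Caucasian patients", and to evaluate its accuracy for progression and for complications.

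Section 2 summarises the earlier evidence: "studies performed by Celera had been cross-sectional studies showing that the CRS correlated with histological cirrhosis with an AUROC of 0.73-0.75". Table 1 in the same section has two classes only. In the training cohort they are headed "Low-Risk (Stage 0) (N=157" and "High-Risk (Stage 3-4) (N=263"; in the validation cohort, "Low-Risk (Stage 0) (N=14" and "High-Risk (Stage 3-4) (N=140". Stages 1 and 2 do not appear.

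Section 4 states that the study "will include patients with bridging fibrosis as well as those with cirrhosis". It names no group with earlier disease.

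In section 5, Stage 1A is headed as validation and has two endpoints: "Cirrhosis on baseline biopsy", and progression to cirrhosis at M24 or M48 among patients without it at baseline. The measures are AUC, sensitivity, specificity, PPV and NPV. No target value is given for any of them. The Naïve Bayes formula, also in section 5, names its two classes cirrhosis and no cirrhosis, with weights 0.626 and 0.374.

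**The concern.** The word cirrhosis carries two meanings. In the score and its published performance it stands for Stage 3-4, set against Stage 0. In Stage 1A it stands for histological cirrhosis, set against bridging fibrosis. Under the natural reading of the stages, the Stage 1A comparators belong to the class that the score was trained to call cirrhosis.

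At stake is how the result is read. A reader told that the score has an AUROC of 0.73-0.75 for histological cirrhosis, and that HALT-C validates it, will set the HALT-C AUC, specificity and NPV beside Table 1. These are different contrasts with different comparators. A low AUC could be taken as refuting a score that performs exactly as it did before, and the HALT-C specificity and NPV would have no counterpart in Table 1.

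**Working it through.** **1. Which contrast gives 0.73-0.75?** The cumulative counts in Table 1 imply 11 score bins (five below 0.50, one from 0.50 to 0.70, five above 0.70). From lowest to highest:

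- Training, Stage 0: 4, 12, 11, 19, 25, 51, 7, 17, 2, 9, 0 (sum 157)
- Training, Stage 3-4: 0, 2, 1, 6, 18, 78, 31, 71, 10, 36, 10 (sum 263)
- Validation, Stage 0: 1, 2, 3, 0, 0, 5, 0, 2, 0, 1, 0 (sum 14)
- Validation, Stage 3-4: 0, 2, 6, 2, 7, 48, 21, 24, 5, 21, 4 (sum 140)

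AUC = (pairs in which the Stage 3-4 patient is in the higher bin + half the tied pairs) / all pairs.

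- Training: (27,851 + 6,345/2) / (157 × 263 = 41,291) = 0.751; stated 0.75.
- Validation: (1,251 + 331/2) / (14 × 140 = 1,960) = 0.723; stated 0.73.

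Binning alone allows 0.675-0.828 and 0.638-0.807. Both stated figures are reproduced as Stage 3-4 versus Stage 0.

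**2. What do the formula classes mean?** 263/(263 + 157) = 0.626 and 157/420 = 0.374. These are the two weights, so the class labelled cirrhosis is Stage 3-4 and the class labelled no cirrhosis is Stage 0. This step needs no model.

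**3. What AUC should Stage 1A be expected to give?** Table 1 pools Stages 3 and 4 and does not say how the score differs between them, so this step rests on assumptions. Take bridging fibrosis as Stage 3 and cirrhosis as Stage 4.

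- *No difference within the high-risk class:* AUC = 0.50.
- *Linear gradient:* scores normal with equal variance, mean rising by k per stage. With π the share of Stage 4 in the high-risk class, solve (1 − π)Φ(3k/√2) + πΦ(4k/√2) = 0.73 or 0.75. For π from 0.2 to 0.7, the Stage 4 versus Stage 3 AUC, Φ(k/√2), is 0.566-0.576 (from 0.73) or 0.573-0.584 (from 0.75), about 0.57-0.58. As a hand check, √2·Φ⁻¹(0.73) = 0.867; with a mean high-risk stage of 3.5, k = 0.867/3.5 = 0.248 and Φ(0.248/√2) = 0.570.
- *What 0.73-0.75 would require:* over the same range of π, an AUC of about 0.79-0.89 for Stage 4 versus 0, but only about 0.58-0.71 for Stage 3 versus 0. That is possible, but a marked departure from a common high-risk class.

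**4. Precision.** The protocol gives only an upper limit of 670 samples, with no count by race or by cirrhosis. Hanley-McNeil standard errors under assumed sizes:

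| Patients (assumed) | Cirrhosis (assumed) | SE at AUC 0.57 | 95% interval |
|---|---|---|---|
| 300 | 30% | 0.037 | 0.50-0.64 |
| 300 | 50% | 0.033 | 0.51-0.63 |
| 670 | 30% | 0.025 | 0.52-0.62 |
| 670 | 50% | 0.022 | 0.53-0.61 |

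At a true AUC of 0.50 the SE is 0.022-0.036. In all these cases the interval lies below 0.73.

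**5. Specificity.** Against Stage 0 at the 0.50 cut-off it is 71/157 = 45.2% (training) and 6/14 = 42.9% (validation). If bridging fibrosis shares the Stage 3-4 score distribution, specificity against bridging fibrosis is the share of that class below 0.50: 27/263 = 10.3% and 17/140 = 12.1%.

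**The case against.** The strongest reply is that the protocol sets no performance target for HALT-C. The 0.73-0.75 figure is background, and section 5 lists measures without a threshold. This stands. A reader might infer that an AUC below 0.73 would be declared a failed validation; no text says so.

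A reader might also infer that 0.73-0.75 cannot be reached, or that Table 1 itself implies about 0.57. Neither is supported. Table 1 is silent on Stage 4 versus Stage 3, the 0.57-0.58 comes from an assumed linear model, and 0.73 is arithmetically possible. Nor does the protocol name its staging scale, so placing every bridging-fibrosis patient in the high-risk class is an assumption. The absence of a named Stage 0 comparator does not depend on it.

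Section 3 makes a second proposal conditional on encouraging results from this one. It is tempting to say that a low Stage 1A AUC would block that work, but the condition is not tied to that AUC, and the second proposal concerns new scores for decompensation and HCC.

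Finally, the protocol is partly open about the matter. Table 1's headers show the stages, section 2 describes a separate serial-biopsy study starting from F0-F1, section 1 uses evaluate rather than validate for progression, and section 6 expects most patients to be predicted cirrhotic. Comparing cirrhosis with bridging fibrosis is a legitimate question here. All this limits the severity. It does not supply the missing statement that the contrast has changed, and Stage 1A puts both endpoints under validation.

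**Conclusion.** The point holds as one of labelling and interpretation. Without any modelling, the earlier AUROC is for Stage 3-4 versus Stage 0, the formula classes carry the same meaning, and HALT-C as described has no Stage 0 comparator. Stage 1A therefore cannot confirm or refute the earlier AUROC, specificity or NPV.

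The size of the expected shortfall is conditional. It takes bridging fibrosis as Stage 3, then either no gradient within the class (0.50) or a linear equal-variance binormal gradient (about 0.57-0.58), with SE about 0.02-0.04 for an assumed 300-670 patients and 30-50% cirrhosis. An AUC near 0.73-0.75 should not be expected, but it is not ruled out.

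The harm is a result misread against the wrong comparator, not failure of a stated criterion. It should be fixed, but it does not invalidate the planned analyses.

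**What to change.** 1. In section 2, describe the earlier AUROC of 0.73-0.75 as Stage 3-4 versus Stage 0. In section 5, define the two formula classes in the same way.
2. In the first primary aim and in Stage 1A, label cirrhosis versus bridging fibrosis, and progression from bridging fibrosis, as a new evaluation within advanced fibrosis. Judge the AUC against 0.50, not against 0.73-0.75, and state how bridging fibrosis maps to the Table 1 stages.
3. Report, with confidence intervals, the share of HALT-C Caucasian patients with CRS not below 0.50 and the share above 0.70, beside the Table 1 sensitivities (87.9-89.7% and 53.6-60.1%). Present this as a check of sensitivity only. It depends on the mix of Stages 3 and 4, and it does not show discrimination: (157 − 71)/157 = 86/157, about 55% of Stage 0 training patients, also score 0.50 or more.
4. State that the Table 1 specificity, NPV and AUROC cannot be validated in this cohort.

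The cost is protocol wording and one descriptive table, with no new data. The downside is a more modest stated aim.

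### Nothing requires the Stage 2 and Stage 3 scores to be locked before their developer holds HALT-C outcomes, so the independence of those two validations is not assured

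*Protocol*

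**What the plan says.** Section 5 of the protocol fixes who receives what. NERI's data set "will be created by NERI and sent to Celera for analysis". It holds fibrosis scores at baseline, M24 and M48, and its last item is "e) Occurrence of clinical outcomes". Celera also gets the samples: "250 ng genomic DNA from each eligible patient will be sent to Celera for genotyping". On linkage: "DNA samples and dataset will be de-identified and coded using subject number only".

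The Data analyses part of Section 5 sets the stages. The first uses the existing score: "Stage 1A: Validate the current Caucasian CRS with 7 SNPs plus gender in Caucasian and African American patients from HALT-C trial in predicting" baseline cirrhosis and later progression. Stage 2 validates an optimized Caucasian score in HALT-C Caucasian and African American patients once it is available, expected by June 2007. More than 600 SNPs around the original seven are under evaluation for it: "These SNPs will be incorporated into the modeling process to obtain a more optimized Caucasian CRS signature". Stage 3 does the same for an African American score in HALT-C African Americans, if a signature is found; a preliminary result is expected in August 2007.

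Section 7 assigns the work: "Biostatisticians at Celera will perform the analysis, the final results will be verified by statisticians at NERI". The undertaking in Part I gives the default: "the data analysis for this proposal will be performed by NERI (unless otherwise approved by the HALT-C study").

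**The concern.** An external validation carries weight because the score was final before anyone who could alter it saw the outcomes of the test patients. Here the party still building two scores is also the party that holds linked genotypes and outcomes for the patients in whom those scores will be tested. If HALT-C results influenced the choice of SNPs, their 0/1 coding, the conditional probabilities or the cutoffs, the reported AUC, sensitivity and specificity for Stages 2 and 3 would be optimistic. That optimism could not be taken out afterwards.

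HALT-C matters as a test set. The earlier validation cohort in Table 1 has only 14 low-risk patients, so its specificity estimates are weak. Section 3 recognises the principle for a different purpose: it asks for external cohorts for any new score that predicts decompensation or HCC.

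**Working it through.** The protocol states no figure on this point, so the main check sets its provisions side by side.

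**1. Access.** Section 5 sends outcomes and DNA to Celera under one subject number. De-identification protects the patients; it does not withhold outcomes from the developer.

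**2. Order in time.** Stage 1 uses the current score, while Stages 2 and 3 wait for scores still to come. It is a natural inference that Celera will hold the Stage 1 outcomes while those scores are unfinished. It remains an inference, because no date for the data transfer is given.

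**3. Same patients.** Stages 2 and 3 name HALT-C patients who also serve in Stage 1. No part is set aside.

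**4. Safeguard.** Section 7 provides verification of final results. Recomputing a final AUC confirms the arithmetic. It cannot be relied on to show when, or on what evidence, the score was settled. No lock, deposit or staged release is stated.

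**5. Is Stage 1 affected?** The CRS formula uses prior weights 0.626 and 0.374. Table 1 gives a training cohort of 263 high-risk and 157 low-risk patients:
- 263 / (263 + 157) = 263 / 420 = 0.626
- 157 / 420 = 0.374

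The weights are those of Celera's training cohort. The seven-SNP score predates this use of HALT-C, so Stage 1 lies outside the concern.

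**6. Illustration of size, if selection on HALT-C outcomes did occur.** Suppose K signatures with true AUC 0.50 are compared and the best is kept.
- Null standard error: SE = √[(N + 1) / (12 · n1 · n0)], with n1 patients with cirrhosis and n0 without.
- Expected best AUC = 0.50 + m(K) · SE, where m(K) is the expected maximum of K independent standard normals; m(20) ≈ 1.87.
- From the protocol: N up to 670 (Part III). Assumed: 30 to 50% with cirrhosis, 100 to 150 African Americans, and K. The figure of over 600 counts SNPs, not candidate signatures, and so does not give K.

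Worked case, N = 670 and 40% cirrhosis: n1 = 268, n0 = 402, SE = √[671 / (12 · 268 · 402)] = 0.0228. With K = 20 the expected best AUC is 0.50 + 1.87 · 0.0228 = 0.543.

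| Patients | SE over 30–50% cirrhosis | K = 5 | K = 20 | K = 100 |
|---|---|---|---|---|
| 670 | 0.022–0.024 | 0.53 | 0.54–0.55 | 0.56 |
| 100–150 (assumed) | 0.047–0.063 | 0.56–0.57 | 0.59–0.62 | 0.62–0.66 |

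Real candidates would share loci and markers. With a common correlation ρ between candidates, the excess over 0.50 shrinks by √(1 − ρ). For the worked case the excess of 0.043 becomes 0.043 · 0.707 = 0.030 at ρ = 0.5 and 0.043 · 0.316 = 0.014 at ρ = 0.9, that is, AUCs of 0.530 and 0.514.

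**The case against.** The strongest reply is that holding data is not the same as training on it. Section 5 names other development material: Celera's own fine mapping for the optimized score, and its genome scan data with 293 African American patients of its own for the other. No sentence says that HALT-C outcomes will enter either score, and release might come after both scores are final. This stands. A reader might infer that Stages 2 and 3 are already development rather than validation; the protocol does not support that.

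Two further inferences also fail:
- Part I and Section 7 might seem to contradict each other on who analyses. They do not: Part I allows another arrangement if HALT-C approves it, and this document is the proposal put forward for approval.
- The provision for genotyping additional SNPs might look like a loophole. A score that contains new SNPs could not be tested without genotyping them.

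It can also be said that a lock rule may sit in an analysis plan or in HALT-C policies that are not at hand. That is possible, and it is a reason for moderate wording. But the release of outcomes to the developer and the division of work are fixed in this protocol, and a later document cannot undo a release already made.

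Last, Stage 1 addresses the primary aims with a fixed score, and Stage 3 is a conditional secondary aim. This limits the reach of the point to Stages 2 and 3.

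**Conclusion.** The concern holds in limited form. The protocol gives the developer linked genotypes and outcomes, apparently while two scores are unfinished, and then has those scores tested in the same patients with no requirement to lock them first. The independence of Stages 2 and 3 is therefore unprotected; it is not shown to be lost. Stage 1 is unaffected.

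The size cannot be derived from the protocol. The AUC figures show only what selection could do if it happened, under assumed prevalence, group size, number of candidates and independence between them. On those assumptions the risk is greater for African Americans, because the group is taken to be small. The AUROCs of 0.73 to 0.75 that the protocol reports for the current score compare Stage 0 with Stage 3–4 disease, so they are no direct yardstick for these figures.

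**What to change.** Add to Sections 5 and 7:

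- Each final Stage 2 and Stage 3 score (SNP list, 0/1 coding, conditional probabilities and cutoffs) is deposited with NERI, dated, before Celera receives HALT-C outcomes.
- If a score is not ready when Stage 1 is due, Celera returns genotypes and CRS values. NERI merges the outcomes, computes performance and returns summary results only. This is consistent with the Part I default.
- Any score finalised after Celera has seen HALT-C outcomes is reported as development or exploratory work, not as validation.

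The cost is some additional programming at NERI, or a delay in Celera's access to patient-level outcomes. No extra patients or samples are needed. The step has to be taken before the data set is released, because the protection cannot be restored later.
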